9 STUDY IMPLEMENTATION

9.1 Study Design

This is a Phase 3, randomized, double-blind, active-controlled, parallel-group, multicenter study. A schematic of the study design is shown in [Figure 9-1](#).

Figure 9-1 Schematic of the Study Design

IVA: ivacaftor; N: number of subjects; TC: triple combination; TEZ: tezacaftor

Note: The Safety Follow-up Visit is not required for subjects who complete the Week 4 Visit and have enrolled in an open-label study within 28 days after the last dose of study drug (Section 9.1.4).

Study drug is defined in Section 10.

All subjects entering the TEZ/IVA Run-in Period will receive TEZ 100 mg once daily (qd)/IVA 150 mg every 12 hours (q12h). Following completion of the TEZ/IVA Run-in Period, approximately 100 subjects will be randomized (1:1) to the TC arm or TEZ/IVA arm for the Treatment Period. The planned dosages for the Treatment Period are shown in Table 9-1. Randomization will be stratified; details are provided in Section 9.2.

Table 9-1 Treatment Period Arms and Dosages

Treatment Arm	VX-659 Dosage	TEZ Dosage	IVA Dosage
TC	240 mg qd	100 mg qd	150 mg q12h
TEZ/IVA	0 mg	100 mg qd	150 mg q12h

IVA: ivacaftor; q12h: every 12 hours; qd: once daily; TC: triple combination; TEZ: tezacaftor

Note: Study drug administration is described in Section 9.6.

Study visits and assessments to be conducted are shown in Table 3-1 and Table 3-2. All visits will occur within the windows specified.

9.1.1 Screening

The Screening Period (Day -56 through Day -29) will occur within 28 days before the first dose of study drug in the Run-in Period.

Screening assessments will be used to confirm that subjects meet the eligibility criteria. The investigator (or an appropriate authorized designee) will obtain informed consent and assent, if applicable, from each subject before any study procedure takes place.

9.1.1.1 Repetition of Screening Assessment(s)

Screening assessments may be repeated once to establish study eligibility. If repeat values of the individual assessment(s) are within the eligibility criteria and completed within the screening window, then the subject is eligible for the study.

9.1.1.2 Rescreening

Subjects may be rescreened once. If a subject is rescreened, all screening assessments will be repeated, except for:

- *CFTR* genotyping
- Follicle-stimulating hormone (FSH) level (if serum FSH level was in the postmenopausal range as determined by the laboratory performing the test during prior screening)
- G6PD activity test
- Ophthalmologic examination (if performed within 3 months of the date of informed consent, for subjects <18 years of age)

If a subject is rescreened, a new screening window will begin when the first rescreening assessment has been initiated.

9.1.1.3 Extension of Screening Period Window

A subject may have the Screening Period window extended by 2 weeks for the following reasons:

- Repetition of the Screening Period assessments (Section 9.1.1.1)
- Unexpected operational or logistic delays, or to meet the eligibility criteria
- Scheduling of ophthalmologic examination (for subjects <18 years of age on the date of informed consent, [Section 11.7.6](#))

9.1.2 Tezacaftor/Ivacaftor Run-in Period

The TEZ/IVA Run-in Period has a 4-week duration and is designed to establish a reliable on-treatment (TEZ/IVA) baseline for the Treatment Period. The first dose of open-label TEZ/IVA will be administered at the Day -28 Visit. The last dose of open-label TEZ/IVA will be administered in the evening on Day -1 (1 day before the Day 1 Visit).

On Day -14, spirometry and SwCl will be assessed. The Day -14 spirometry assessment will be used for stratification of randomization ([Section 9.2](#)).

Subjects who prematurely discontinue study drug treatment during the Run-in Period will not be randomized or participate in the Treatment Period ([Section 9.1.5.1](#)).

9.1.3 Treatment Period

The Treatment Period will be randomized, double-blind, and active-controlled. It will last approximately 4 weeks (Day 1 to Week 4). Study drug administration details are provided in [Section 9.6](#).

Randomization will occur before the first dose of study drug during the Treatment Period and may occur on either Day -1 or Day 1. Randomization and stratification details are provided in [Section 9.2](#).

To enter the Treatment Period, subjects must have stable CF disease (as judged by the investigator) and have remained on a stable CF treatment regimen during the TEZ/IVA Run-in Period. Female subjects of childbearing potential also must have a negative pregnancy test at Day 1 before receiving randomized study drug. If these conditions are not met (for example, if the subject has an acute upper or lower respiratory infection, PEx, or changes in therapy [including antibiotics] for sinopulmonary disease within 28 days before the Day 1 Visit [first dose of study drug in the Treatment Period]), subjects may be rescreened once ([Section 9.1.1.2](#)) and re-enter the Run-in Period on Day -28.

Subjects who prematurely discontinue study drug treatment during the Treatment Period will remain in the study from the time of discontinuation of study drug treatment through the last scheduled study visit and complete the assessments for all study visits, as described in [Section 9.1.5.2](#).

9.1.4 Follow-up

The Safety Follow-up Visit will occur approximately 28 days after the last dose of study drug for subjects who complete study drug dosing and for subjects who prematurely discontinue study drug dosing, as described in [Section 9.1.5](#).

An open-label study will be available for subjects who complete the Week 4 Visit and are eligible. The Safety Follow-up Visit is not required for subjects who complete the Week 4 Visit and enroll in an open-label study within 28 days after the last dose of study drug.

9.1.5 Early Termination of Treatment

If a subject prematurely discontinues study drug treatment, an Early Termination of Treatment (ETT) Visit should be scheduled as soon as possible after the decision to discontinue treatment. Subjects who prematurely discontinue treatment will also be required to complete the Safety Follow-up Visit, approximately 28 days after their last dose of study drug. The assessments performed at the Safety Follow-up Visit are listed in [Table 3-2](#).

If the ETT Visit occurs 3 weeks or later following the last dose of study drug, then the ETT Visit will replace the Safety Follow-up Visit, and a separate Safety Follow-up Visit will not be required.

If a subject withdraws from the study and also withdraws consent or assent, no further assessments will be performed. Vertex may retain and continue to use any data and samples collected before such withdrawal of consent or assent.

9.1.5.1 Discontinuation During the Run-in Period

Subjects who prematurely discontinue study drug treatment during the Run-in Period will not be randomized or participate in the Treatment Period. These subjects will complete an ETT Visit and Safety Follow-up Visit (as applicable; see [Section 9.1.5](#)). The Safety Follow-up Visit will be their last visit in the study.

9.1.5.2 Discontinuation During the Treatment Period

Subjects who prematurely discontinue study drug treatment during the Treatment Period will continue to complete all scheduled study visits for assessments following completion of the ETT Visit, as detailed in [Table 3-2](#).

These subjects will complete an ETT Visit and Safety Follow-up Visit (as applicable; see [Section 9.1.5](#)). The Safety Follow-up Visit will be their last visit in the study.

9.1.6 Lost to Follow-up

A subject will be considered lost to follow-up if both of the following occur:

- The subject misses 2 consecutive study visits (telephone contact and/or clinic visit) and is subsequently unable to be contacted by telephone (3 documented attempts by telephone within 2 weeks following the second missed visit)
- The subject does not respond within 2 weeks to a registered letter sent after the 3 attempted telephone contacts.

9.1.7 Completion of Study Participation

Completion of study participation for each individual subject is defined as one of the following:

- For subjects who complete the Treatment Period and enter an open-label study within 28 days of the Week 4 Visit: the Week 4 Visit
- For subjects who complete the Treatment Period and do not enter an open-label study within 28 days of the Week 4 Visit: the Safety Follow-up Visit
- For subjects who prematurely discontinue study drug treatment during the Treatment Period but do not withdraw consent (and assent, as applicable): The ETT or Safety Follow-up Visit (if required)
- For subjects who prematurely discontinue study drug treatment during the TEZ/IVA Run-in Period but do not withdraw consent (and assent, as applicable): the ETT or Safety Follow-up Visit (if required)
- For subjects who withdraw consent or assent: date of withdrawal of consent or assent, whichever is earlier ([Section 9.9](#))

If subjects are lost to follow-up ([Section 9.1.6](#)), the date of completion of study participation will be defined as the date of the last contact.

The end of study is defined in [Section 13.2.8](#).

9.1.8 Independent Data Monitoring Committee

This study will be monitored by an independent data monitoring committee (IDMC), which will conduct periodic reviews of safety data from the study ([Section 12.3.6.2](#)). Procedural details of the IDMC structure and function, frequency of meetings, and data planned for review will be included in the IDMC charter. The IDMC charter will be finalized before the first subject is screened.

9.2 Method of Assigning Subjects to Treatment Groups

Subjects will be randomized (1:1) to the TC VX-659/TEZ/IVA arm or to the TEZ/IVA arm. Randomization will be stratified by ppFEV₁ determined during the TEZ/IVA Run-in Period (Day -14 assessment; <70 versus ≥70) and age at the Screening Visit (<18 versus ≥18 years of age). If the Day -14 ppFEV₁ value is not valid or not available, the most recent available ppFEV₁ value will be used for stratification.

An interactive web response system (IWRS) will be used to assign subjects to treatment. The randomization code list will be produced by Vertex Biometrics or a qualified randomization vendor.

9.3 Rationale for Study Design and Study Drug Regimens

9.3.1 Study Design

This Phase 3 study will assess the efficacy, PD, safety, and PK of VX-659/TEZ/IVA TC therapy in subjects with CF who have an F/F genotype.

A randomized, double-blind, controlled study design was selected to ascertain the effects of VX-659/TEZ/IVA while avoiding observer bias. TEZ/IVA is considered an appropriate active control since the efficacy and safety of TEZ/IVA in F/F subjects have been demonstrated in Study VX14-661-106 (Study 661-106).¹⁴ Study 661-106 met its primary endpoint of absolute change in ppFEV₁ through Week 24, with a 4.0 percentage point treatment difference between TEZ/IVA and placebo. In Study 661-106, TEZ/IVA was well tolerated and no safety concerns attributable to TEZ/IVA were identified.

A 4-week TEZ/IVA Run-in Period was incorporated into this study to establish a reliable on-treatment (TEZ/IVA) baseline for comparison during the Treatment Period.

[figure not shown]
The study will have a 4-week treatment duration because previous studies of CFTR modulators (IVA, LUM/IVA, and TEZ/IVA) have demonstrated that efficacy related to lung function (ppFEV₁) can be reliably established using an endpoint at Week 4. In these studies, rapid improvements in ppFEV₁ are observed by Day 15, with a separation between the active treatment and placebo groups that is sustained through 24 weeks of treatment. These studies were conducted in patients with different genotypes, baseline ppFEV₁, and age groups, using CFTR modulators that had different magnitudes of response.

The extent of response to CFTR modulator treatment may depend on the subject's ppFEV₁ value (an index of disease severity) before the start of TC study drug dosing. Some subjects in this study may be receiving treatment with LUM/IVA or TEZ/IVA at Screening, while some subjects may not be receiving treatment with CFTR modulators. Therefore, randomization will be stratified by ppFEV₁ value determined during the TEZ/IVA Run-in Period after at least 13 days of TEZ/IVA (Day -14 assessment). Randomization will also be stratified by age at screening. This will ensure a balanced evaluation of adult and pediatric subjects.

9.3.2 Study Drug Dose

VX-659 Dosage

A VX-659 dose of 240 mg qd was selected for the current study based on an assessment of the benefit-risk profile from the ongoing Phase 2 Study VX16-659-101 (Study 659-101) Part 1,

TEZ and IVA Dosages

TEZ will be administered as 100 mg qd and IVA will be administered as 150 mg q12h. This is the approved dosing regimen for Symdeko, which is now approved in the US.

[figure not shown]
9.3.3 Rationale for Study Population

This study will enroll CF subjects with the F/F genotype. F/F patients have continuing unmet need despite the availability of CFTR modulators and are expected to respond to a TC regimen of VX-659/TEZ/IVA based on results from Phase 1 and 2 studies in subjects with a single responsive *F508del* allele (F/MF genotypes) and in vitro experiments in relevant human F/F cell-based model systems.

The VX-659 Phase 2 clinical safety and efficacy data support the enrollment of pediatric subjects ≥ 12 and < 18 years of age in this study.

9.3.4 Rationale for Study Assessments

The PD and efficacy endpoints being evaluated (SwCl, spirometry, and patient-reported outcomes) are widely accepted and generally recognized as reliable, accurate, and relevant to the study of individuals with CF. SwCl was evaluated in the registration study of IVA (Kalydeco), and spirometry and CFQ-R assessments were evaluated in the registration studies of IVA (Kalydeco) and LUM/IVA combination therapy (Orkambi).

[REDACTED]

[REDACTED]

[REDACTED]

9.4 Study Restrictions

9.4.1 Prohibited Medications

Table 9-2 lists prohibited medications. A non-exhaustive list of study prohibitions and cautions for medication will be provided in the Study Reference Manual.

Table 9-2 Prohibited Medications

Medication	Timing of Restriction		Rationale
	Start of Restriction	End of Restriction	
Moderate and strong CYP3A or CYP2C9 inducers	None allowed within 14 days before the first dose of the study drug on Day -28	None allowed through completion of study participation	VX-659, TEZ, and IVA are metabolized extensively via CYP3A4. VX-659 is also metabolized by CYP2C9. Therefore, use of moderate and strong inducers of CYP3A or CYP2C9 and moderate and strong inhibitors of CYP3A, which have the potential to alter the exposure of VX-659, TEZ, or IVA, will be prohibited.
Moderate and strong CYP3A inhibitors (except ciprofloxacin) ^a	None allowed within 14 days before the first dose of the study drug on Day -28	None allowed through completion of study participation	
Sensitive OATP1B1 substrates	None allowed within 14 days before the first dose of the study drug on Day -28	None allowed through completion of study participation	VX-659 is a potential inhibitor of the hepatic transporter OATP1B1. Therefore, sensitive substrates of OATP1B1, such as HMG-CoA reductase inhibitors (“statins”) are prohibited during treatment.
Non-Vertex CFTR modulators (investigational or approved)	None allowed within 28 days or 5 terminal half-lives (whichever is longer) before screening	None allowed through completion of study participation	These agents may confound the results of this study.
Vertex CFTR modulators (investigational or approved), except for study drugs	None allowed from the first dose of study drug on Day -28	None allowed until after the last dose of study drug	These agents may confound the results of this study.

CYP: cytochrome P450; IVA: ivacaftor; OATP1B1: organic anion transporting polypeptide 1B1; TEZ: tezacaftor

^a Ciprofloxacin is not a moderate CYP3A inhibitor on the basis of results of a drug-drug interaction study conducted with IVA, a sensitive CYP3A substrate (Kalydeco [ivacaftor] US Package Insert).

9.4.2 Exposure to Sunlight

Subjects will take appropriate measures to minimize exposure to UV radiation (e.g., prolonged sunlight, tanning booths) from Day 1 through completion of study participation.

9.5 Prior and Concomitant Medications

Information regarding prior and concomitant medications, including CF medications, other medications, and herbal and naturopathic remedies, will be collected from each subject’s source documentation for medications taken within 56 days before the Screening Visit through completion of study participation, as defined in [Section 9.1.7](#).

For subjects who are screened but are not subsequently randomized into the Treatment Period, details of prior medication will be documented only in the subjects’ source documents.

- Subjects should remain on a stable treatment regimen for their CF from 28 days before the TEZ/IVA Run-in/Day -28 through completion of study participation. Stable treatment regimen is defined as the current treatment regimen for CF that subjects have been following

for at least 28 days before the TEZ/IVA Run-in/Day -28. Subjects may remain on Vertex CFTR modulators (investigational or approved) during the Screening Period and may transition directly to the TEZ/IVA Run-in/Day -28 without a washout (Table 9-2). Subjects should not initiate long-term treatment with new medication from 28 days before the TEZ/IVA Run-in/Day -28 through completion of study participation. Guidelines for stable treatment regimens for CF are as follows:

- o Subjects who are taking inhaled tobramycin or other chronically inhaled antibiotics should remain on that regimen throughout the study.
 - o Subjects who cycle onto and off of an inhaled antibiotic should continue on their prior schedule. The timing of the first dose of study drug on the Day 1 Visit should be synchronized as closely as possible (e.g., not more than ± 3 days) to the first day in the cycle onto the inhaled antibiotic.
 - o Subjects who alternate between 2 different inhaled antibiotics should remain on the same cycling schedule during the study. The timing of the first dose of study drug on the Day 1 Visit should be synchronized as closely as possible (e.g., not more than ± 3 days) to the first day in the cycle onto 1 of the inhaled antibiotics.
- Subjects may receive doses of prednisone or prednisolone of up to 10 mg/day chronically, or up to 60 mg daily for up to 5 days.
 - Information about bronchodilator use during the study will be collected and documented. Subjects who are using a bronchodilator must have their spirometry assessments performed according to the guidelines provided in Section 11.6.1.

9.6 Administration

9.6.1 Dosing

Study drug will be administered orally. All subjects will receive the same number of tablets each day to maintain the blind. Additional information is provided in the Pharmacy Manual.

Study drug will be administered with a fat-containing meal or snack, such as a standard “CF” meal or snack or a standard meal.

1. It is recommended that the dose be taken within 30 minutes of the start of the meal or snack.
2. Study drug will be administered as fixed-dose combination (FDC) tablet(s) (e.g., 2 TC or matching placebo tablets; 1 TEZ/IVA or matching placebo tablet) in the morning and as 1 IVA tablet in the evening. For each subject, doses of study drugs will be taken at approximately the same time (± 2 hours) each day.
3. The date, amount taken, and time of study drug administration, including whether food was taken with each dose, will be recorded for the 2 doses before PK sample collection and the dose received on the morning of PK sample collection (if applicable).
4. On days of scheduled visits, the morning dose of study drug (TC, TEZ/IVA, or placebo) will be administered at the site after predose assessments have been completed. A meal or snack will be provided by the site for the morning dose of TC, TEZ/IVA, or placebo.
5. If a subject’s scheduled visit is to occur in the afternoon, the following guidelines must be used:

- If the dose in the clinic will be within 6 hours of the subject's scheduled morning dose, the subject should withhold their morning dose of TC, TEZ/IVA, or placebo and the morning dose will be administered in the clinic.
 - If the dose in the clinic will be more than 6 hours after the subject's scheduled morning dose, the subject should take the morning dose of TC, TEZ/IVA, or placebo at home.
6. Subjects will be instructed to bring all used and unused materials associated with the study drug to the site; study drug will be dispensed at each visit, as appropriate.

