3 SCHEDULE OF ASSESSMENTS

Table 3-1 and Table 3-2 provide the schedule of assessments for the study.

All visits are to be scheduled relative to the Day 1 Visit (first dose of randomized study drug in the Treatment Period). For example, the Week 4 (± 5 days) Visit would occur after 4 weeks of study drug administration in the Treatment Period has been completed.

The Cystic Fibrosis Questionnaire–Revised (CFQ-R), [REDACTED] must be completed before any other assessment at relevant clinic visits. Remaining assessments may be performed in any order when more than 1 assessment is required at a particular time point. All assessments will be performed before study drug dosing (Section 9.6.1), unless noted otherwise.

Table 3-1 Study VX17-659-103: Screening

Event/Assessment	Screening Period (Day -56 Through Day -29)
ICF and assent (when applicable)	X
Inclusion and exclusion criteria review	X
Demographics	X
Medical history	X
CFQ-R ^a	X
CFTR genotype ^b	X
G6PD activity test	X
FSH ^c	X
Serum pregnancy test (all females of childbearing potential) ^d	X
Hematology	X
Coagulation	X
Serum chemistry	X
Urinalysis	X
Weight and height ^e	X
Ophthalmologic examination ^f	X
Complete physical examination	X
Vital signs ^g	X
Pulse oximetry ^g	X
Standard 12-lead ECG ^h	X
Spirometry ⁱ	X
Medications review ^j	X
Sweat chloride	X
AEs and SAEs	Continuous from signing of the ICF through completion of study participation

AE: adverse events; CFQ-R: CF-Questionnaire-Revised; FSH: follicle-stimulating hormone; G6PD: glucose-6-phosphate dehydrogenase; ICF: informed consent form; SAE: serious adverse event

^a The CFQ-R must be completed before the start of any other assessments scheduled for that visit.

^b *CFTR* genotyping will be performed for all subjects. If the screening *CFTR* genotype result is not received before Day -28, a previous *CFTR* genotype laboratory report may be used to establish eligibility. Subjects who have been enrolled and whose screening genotype does not confirm study eligibility must be discontinued from the study ([Section 9.9](#)).

^c FSH will be measured for any suspected postmenopausal female with at least 12 months of continuous spontaneous amenorrhea. Serum FSH levels must be in the postmenopausal range, as determined by the laboratory performing the test, to be considered postmenopausal.

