^c The Safety Follow-Up Visit is required for all subjects, unless the subject completes the Week 4 Visit and has enrolled in a separate open-label study within 28 days after the last dose of study drug (Section 9.1.4). If an ETT Visit occurs 3 weeks or later following the last dose of study drug, then the ETT Visit replaces the Safety Follow-up Visit (Section 9.1.5).

^d To enter the Treatment Period, conditions for entry (Section 9.1.3) must be satisfied.

^e The CFQ-R, [REDACTED] must be completed before any other assessments scheduled at relevant visits. Refer to Section 11.6.2 and [REDACTED]

^f Weight and height will be measured with shoes off. Following screening, height will be collected only for subjects ≤21 years of age on the date of informed consent.

^g Abbreviated and complete physical examinations are defined in Section 11.7.3. Symptom-directed physical examinations will occur at any time during the study if deemed necessary by the investigator.

^h Any female subject who does not meet the criteria for non-childbearing potential is considered to be of childbearing potential and must have pregnancy testing at the indicated time points. A definition of non-childbearing potential is provided in Section 11.7.7.1.

ⁱ All standard 12-lead ECGs will be performed after the subject has been at rest for at least 5 minutes. ECGs will be collected before dosing (as applicable).

Table 3-2 VX17-659-103: TEZ/IVA Run-in Period, Treatment Period, and Safety Follow-up Visit

Event/Assessment ^a	TEZ/IVA Run-in Period (4 Weeks)		Treatment Period (4 Weeks)			ETT Visit ^b	Safety Follow-up Visit 28 (± 7) Days After the Last Dose of Study Drug (If Applicable) ^c
	Day -28 ± 1 Day	Day -14 (Day -15 to Day -3)	Day 1 ^d	Day 15 ± 3 Days	Week 4 ± 5 Days		
Vital signs ^j	X		X	X	X	X	X
Pulse oximetry ^j	X		X	X	X	X	X
Spirometry ^k		X	X	X	X	X	X
Sweat chloride ^l		X	X	X	X	X	
Urinalysis	X		X		X	X	X
Hematology	X ^m		X ^m	X	X	X	X
Coagulation	X ^m		X ^m		X	X	X
Serum chemistry	X ^m		X ^m	X	X	X	X
PK sampling ⁿ			X		X	X	

^j Vital signs and pulse oximetry will be collected before dosing and after the subject has been at rest for at least 5 minutes.

^k Spirometry assessments must be performed before study drug dosing (see [Section 9.6.1](#)) and should be performed pre-bronchodilator ([Section 11.6.1](#)) at approximately the same time at each visit.

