^l Sweat chloride collection will occur before study drug dosing ([Section 11.4](#)). At each time point, 2 samples will be collected, 1 from each arm (left and right).

^m Blood samples will be collected before the first dose of study drug in each study period.

ⁿ The Day 1 predose PK sample must be collected before dosing. The Week 4 predose PK sample must be collected within 60 minutes before dosing for subjects who are receiving their first dose of study drug in an open-label study on the same day as the Week 4 Visit. For subjects who are not entering an open-label study on the same day as the Week 4 Visit, the Week 4 sample should be collected approximately 12 hours after the evening dose of IVA before the Week 4 Visit ([Section 11.3.1](#)).

Table 3-2 VX17-659-103: TEZ/IVA Run-in Period, Treatment Period, and Safety Follow-up Visit

Event/Assessment ^a	TEZ/IVA Run-in Period (4 Weeks)		Treatment Period (4 Weeks)			ETT Visit ^b	Safety Follow-up Visit 28 (± 7) Days After the Last Dose of Study Drug (If Applicable) ^c
	Day -28 ± 1 Day	Day -14 (Day -15 to Day -3)	Day 1 ^d	Day 15 ± 3 Days	Week 4 ± 5 Days		
Run-in TEZ/IVA dosing ^q	Day -28 to evening on Day -1						
Run-in TEZ/IVA drug count	X	X	X				
Randomization ^r			X				
Randomized study drug dosing ^s			Day 1 through evening before the Week 4 Visit				
Randomized study drug count			X	X	X	X	
Medications review ^u	Continuous from signing of ICF through completion of study participation						
Treatments and procedures review ^u	Continuous from signing of ICF through completion of study participation						
AEs and SAEs ^{u, v}	Continuous from signing of ICF through completion of study participation						

AE: adverse event; CF: cystic fibrosis; CFQ-R: CF Questionnaire-Revised; ETT: Early Termination of Treatment; GPS: Global Patient Safety; ICF: informed consent form; IV: intravenous; IVA: ivacaftor; PD: pharmacodynamic; ██████████ PK: pharmacokinetic; SAE: serious adverse event; TEZ: tezacaftor;

^q For the Run-in Period, TEZ/IVA should be administered as outlined in [Section 9.6.1](#). On days of scheduled visits, refer to [Section 9.6.1](#) for the timing of dosing relative to the assessments. The final dose during the Run-in Period will be administered on Day -1, the evening before the Day 1 Visit.

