11.4 Pharmacodynamics: Sweat Chloride

SwCl samples will be collected with an approved collection device. Each collection will occur before study drug dosing ([Section 9.6.1](#)). At each time point, 2 samples will be collected, 1 from each arm (left and right). Sweat samples will be sent to a central laboratory for testing and interpretation of results. Specific instructions for the collection, handling, processing, and shipping of SwCl samples to the central laboratory will be provided separately.

See [Section 10.7.1](#) for information about access to SwCl results.

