11.6 Efficacy

11.6.1 Spirometry

Spirometry will be performed according to the American Thoracic Society Guidelines/European Respiratory Society Guidelines¹⁰ and according to the additional guidelines that follow.

Pre-bronchodilator spirometry is defined as spirometry testing performed for subjects who have

- withheld their short-acting bronchodilators (e.g., albuterol) or anticholinergic (e.g., ipratropium bromide [Atrovent®]) for more than 4 hours before the spirometry assessment;
- withheld their long-acting bronchodilator (e.g., salmeterol) for more than 12 hours before the spirometry assessment; and
- withheld their once-daily, long-acting bronchodilator (e.g., tiotropium bromide [Spiriva®]) for more than 24 hours before the spirometry assessment.

During the Screening Period, spirometry assessments may be performed pre- or post-bronchodilator. At all other visits, all spirometry assessments should be performed pre-bronchodilator. During the Treatment Period, spirometry assessments must be performed before study drug dosing ([Section 9.6.1](#)) at approximately the same time at each visit. In the

event that a subject forgets to withhold bronchodilator(s), spirometry should be performed according to the following:

- If a subject's Day 1 spirometry assessment is pre-bronchodilator, but, on a subsequent visit, the subject forgets to withhold bronchodilator use, a post-bronchodilator spirometry assessment will be obtained for that visit only, and the visit will not be rescheduled.
- If, on Day 1, the subject forgets to withhold his/her dose of bronchodilator, spirometry should be performed post-bronchodilator, and all subsequent spirometric measurements (according to the schedule of assessments in [Table 3-2](#)) should be performed post-bronchodilator.
- Each spirometry assessment will be recorded in the source documents as pre- or post-bronchodilator.

All sites will be provided with spirometers to be used for all study assessments. Spirometry data will be transmitted to a centralized spirometry service for quality review. The investigator's assessment of the spirometry results will be used for the screening assessment and determination of eligibility.

See [Section 10.7.1](#) for information about access to spirometry results.

The measured spirometric values listed below will be converted to percent predicted values using the standard equations of GLI.⁹

- FEV₁ (L)

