11.7.4 Pulse Oximetry

Pulse oximetry is a noninvasive measure of oxygen delivery to the tissues and has been correlated with clinical status and lung function. Arterial oxygen saturation by pulse oximetry will be assessed following at least a 5-minute rest and before study drug dosing. At visits when study drug is taken at the site, pulse oximetry will be collected before study drug dosing (Section 9.6.1).

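### At Day -14 and Day 15 visits more than 6 hours after the usual morning dose, the home-dosing rule in Protocol 9.6.1 makes spirometry and sweat chloride post-dose, against the pre-dose rule (minor)

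*Protocol*

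**What the plan says.** **Dosing on visit days.** Protocol 9.6.1 item 4 places the morning dose at the site, after the predose assessments. Item 5 is mandatory for afternoon visits and splits them at 6 hours. Up to 6 hours after the usual morning dose, the subject withholds the dose until the clinic. Beyond 6 hours, "the subject should take the morning dose of TC, TEZ/IVA, or placebo at home".

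**Timing of the tests.** Section 3 gives the general rule: "All assessments will be performed before study drug dosing (Section 9.6.1), unless noted otherwise". The rules for the two tests at issue are:

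- Table 3-2 footnote k: "Spirometry assessments must be performed before study drug dosing".
- Table 3-2 footnote l: "Sweat chloride collection will occur before study drug dosing".
- Section 11.4, on sweat chloride: "Each collection will occur before study drug dosing".
- Section 11.6.1: "During the Treatment Period, spirometry assessments must be performed before study drug dosing". This sentence covers Day 15 but not Day -14.

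Footnotes q and s send the reader to 9.6.1 "for the timing of dosing relative to the assessments".

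**Use of the values.** Day -14 ppFEV1 sets the randomization stratum (Protocol 9.1.2 and 9.2). Day 15 changes enter the repeated-measures models for ppFEV1 and sweat chloride, and treatment differences are reported at each post-baseline visit (Protocol 12.3.3.1 and 12.3.3.2; SAP 9.3.1.2 and 9.3.2.2).

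**The concern.** At a visit booked late enough, a site cannot follow both item 5 and the pre-dose rules. If it follows item 5, a Day 15 value measured a few hours after a dose is compared with a Day 1 baseline measured long after the last dose. Part of the Day 15 change could then reflect time since dose.

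Nothing planned would reveal this afterwards. Item 3 of 9.6.1 requires dose times only around PK sampling, and Table 3-2 schedules no PK sample at Day -14 or Day 15. SAP Appendix A marks the spirometry and sweat chloride baselines as pre-dose but puts no dose-timing condition on the Day 15 window.

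**Working it through.** The plan states no figure on this point. The nearest one, power of about 93%, reproduces with a two-sample *t*-test (difference 5.0, SD 7, two-sided 0.05): 92.9% with 47 per arm and 93.4% with 48 per arm after 5% dropout. It does not depend on dose timing.

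**Step 1: which visits are exposed.** A conflict needs both tests and a morning study dose that could be taken at home.

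| Visit | Spirometry and sweat chloride | Morning dose that could be taken at home | Conflict possible |
|---|---|---|---|
| Day -28 | No | First run-in dose is at the visit | No |
| Day -14 | Yes | Yes | Yes |
| Day 1 | Yes | No: run-in dosing ends the evening before (footnote q) | No |
| Day 15 | Yes | Yes | Yes |
| Week 4 | Yes | No: randomized dosing ends the evening before (footnote s) | No |

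**Step 2: time since dose.** Let T be the usual morning dose time and the visit be at T + h, with h between 6 and 12. Assume that the evening ivacaftor tablet is taken at T + 12, that a home dose is taken at T, and that Day 1 and Day 15 are at the same clock time. The morning tablets contain tezacaftor and ivacaftor, plus VX-659 in the triple-combination arm.

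- Day 1: last tezacaftor is 24 + h hours old; last ivacaftor is 12 + h hours old.
- Day 15 after a home dose: both are h hours old.
- Difference: (24 + h) − h = 24 hours for tezacaftor; (12 + h) − h = 12 hours for ivacaftor.

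With assumed dosing at 08:00 and 20:00 and a 15:00 visit (h = 7), the ages are 31 and 19 hours on Day 1, against 7 and 7 hours on Day 15. At h = 9 they are 33 and 21, against 9 and 9.

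If Day 1 was earlier in the day, the gap shrinks. With Day 1 at the usual dose time (h = 0) and Day 15 at h = 7, it is 24 − 7 = 17 hours for tezacaftor and 12 − 7 = 5 hours for ivacaftor.

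**Step 3: with the dose withheld and h from 0 to 6.** Day 15 is 24 to 30 hours after the morning tablets and 12 to 18 hours after ivacaftor. At the same clock time this equals Day 1 for tezacaftor and ivacaftor, so the difference is 0.

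**Step 4: reach into the Week 4 estimate.** Day 15 values inform the Week 4 difference mainly through subjects with no Week 4 value. At the planned dropout that is 0.05 × 50 = 2.5 per arm, and only those with a late Day 15 visit would matter.

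**The case against.** The strongest reply is that the protocol already names 9.6.1 as the authority on timing. Section 3 allows exceptions and cites 9.6.1. Footnotes k, q and s and Sections 11.4 and 11.6.1 point there too, and item 5 is the specific rule for afternoon visits. It also has a dosing rationale: under 9.6.2.1, a morning dose taken more than 6 but fewer than 12 hours late costs the evening ivacaftor dose, and item 5 uses the same 6-hour limit. So it is too strong to infer that a site has no guidance on which rule prevails; an intended exception is arguable. Item 5 nevertheless says only where the dose is taken, not that these tests may follow it.

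A reader might also see proof of an oversight in the pulse oximetry text, which has an on-site condition: "At visits when study drug is taken at the site, pulse oximetry will be collected before study drug dosing". The documents do not support that inference. The preceding sentence of 11.7.4 and footnote j are unconditional, and footnote i softens the ECG rule separately. The wording is uneven across tests and does not show what was intended for spirometry and sweat chloride.

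Third, the conflict arises only if a site books late. Spirometry is to be at about the same time at each visit. For subjects not rolling over on the day of Week 4, the Week 4 PK sample is due about 12 hours after evening ivacaftor. Together these favor mornings. This makes late visits less likely but does not exclude them, since no PK sample anchors Day -14 or Day 15.

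**Conclusion.** The inconsistency is real but minor, and confidence is moderate because an intended exception cannot be ruled out. Following item 5 as written can put post-dose Day 15 ppFEV1 and sweat chloride values into the models with no required dose time and no flag. The size is known only as clock time: 24 hours for tezacaftor and 12 hours for ivacaftor under the same-clock-time assumption. The documents give neither the share of late visits nor the effect of dose timing on either measure, so no effect size is claimed.

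A reader might infer that the primary result or the testing hierarchy is at risk. The documents do not support this. The tested endpoints are at Week 4, the Day 1 and Week 4 measurements are outside the conflict, and Day 15 reaches the Week 4 estimate only weakly. Nor does the Day -14 timing bias the arm comparison, because it precedes randomization.

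What remains is comparability of some Day 15 records, the reported Day 15 treatment difference and the Day -14 stratification value. The rule is the same in both blinded arms. However, only one arm takes VX-659, so equal timing need not have an equal effect on the Day 15 difference.

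**What to change.** Add to Protocol 9.6.1 item 5:

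*Book Day -14 and Day 15 visits so that the clinic dose falls within 6 hours of the usual morning dose time, and withhold the dose until spirometry and sweat chloride are done. If this is not possible, rebook within the visit window. If rebooking is also not possible, the subject takes the morning dose at home, the tests are still done, and the dose time is recorded and the values flagged as post-dose.*

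The existing windows leave room: Day -15 to Day -3 is 13 days, and Day 15 ± 3 days is 7 days. The last step keeps the Day 15 record without costing the subject the evening ivacaftor dose. Day 1 and Week 4 need no change.

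The cost is one protocol clarification, plus a dose time and a flag in the rare fallback case. There would be fewer late-afternoon slots at two visits, which may be felt most by school-age subjects. With an assumed usual dose at 08:00, the latest clinic dose would be 14:00; with 10:00, it would be 16:00.
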